6.2 Preparation, handling, storage and accountability

Only participants enrolled in the study may use study intervention and only delegated site staff may supply study intervention.

Each site will be supplied with sufficient study intervention for the study on an ongoing basis according to recruitment and allocation to sub-study/indication.

For selected countries and if permitted by local regulations, the investigator may offer to send study intervention from the study site or pharmacy to the participant's home by courier service. The process for sending study intervention from the study site or pharmacy to a participant's home is described in the "Study site/pharmacy instruction for shipment of trial product to participants' homes" document. This document contains detailed instructions for preparing, packaging and setting up the pick-up of study intervention, handover of study intervention from the study site or pharmacy staff to the courier, required temperature monitoring of study intervention, delivery to and receipt of study intervention by the participant. The process for returning study intervention to the study site or pharmacy by courier is also described in this document. Investigators, study site/pharmacy staff and participants who will be involved in shipment of study intervention to the participant's home will be adequately trained in this process.

The investigator or designee must confirm that appropriate temperature conditions have been maintained during transit for all trial products received, and that any discrepancies are reported and resolved before use of the trial products.

All trial products must be stored in a secure, controlled, and monitored (manual or automated) area in accordance with the labelled storage conditions with access limited to the investigator and delegated site staff.

The investigator must inform Novo Nordisk immediately if any trial product has been stored outside specified conditions. The trial product must not be dispensed to any participant before it has been evaluated and approved for further use by Novo Nordisk. Additional details regarding handling of temperature deviations can be found in the Trial Materials Manual (TMM).

The investigator or designee is responsible for trial product accountability and record maintenance (i.e., receipt, accountability and final disposition records).

The investigator or designee must instruct the participant in what to return at next visit. In this study, the participant should bring all trial product back at every visit, if not otherwise instructed.

The investigator or designee must instruct the participant on how to manage the in-use time of the dispensed products.

Drug accountability is performed on Kit ID level.

Destruction of trial products can be performed on an ongoing basis and will be done according to local procedures after accountability is finalised by the site and/or reconciled by the monitor, if not otherwise agreed at the site selection.

All returned (used or un-used), expired or damaged trial products (for technical complaint samples, see Appendix 9 (Section [10.9](#))) must be stored separately from non-allocated trial products. No temperature monitoring is required.

Non-allocated trial products, including expired or damaged products, must be accounted by the site and/or reconciled by the monitor, at the latest at closure of the site.

Korea: Please see local requirements in Appendix 11 (Section [10.11](#)).

6.3 Measures to minimise bias: Randomisation and blinding

All participants will be screened and centrally allocated using the RTSM system and assigned by diagnosis to the relevant treatment according to the allocation schedule. Trial product will be allocated by the RTSM and dispensed by the investigator at the study visits summarised in the flowchart.

All screened participants will receive a unique subject ID at the screening visit using RTSM. The subject ID will be assigned to the participant throughout the study. The subject ID will reflect the sub-study to which the participant has been allocated.

This is an open-label one-armed study with no blinding at site level.

6.4 Study intervention compliance

Drug treatment compliance

Throughout the study, the investigator will remind the participants to follow the study procedures and requirements to encourage participant compliance.

When participants are dosed at the site, they will receive trial product directly from the investigator or designee, under medical supervision. The date and time of each dose administered at the site will be recorded in the source documents.

When participants are dosed at home, compliance with trial product administration will be assessed, and the assessment documented in source documents at each visit where information is available. If any suspicion of non-compliance arises, the site must enter into a dialogue with the participant, re-emphasizing the importance of compliance and uncover barriers to compliance. This dialogue must be documented. Compliance will be assessed by cross checking the following sources and comparing these to the expected use:

- Accountability information; counting returned trial product, comparing number of returned pens with number of dispensed pens, compare number of used pens with the planned dose, visual inspection of pens
- Review of dosing diaries
- Questioning of participants

Trial product injection date, time, dose and injection location will be recorded in the dosing diary until visit 17 (extension period I). From visit 19 to visit 25 and the discontinuation visit (visit 98) (extension period II) trial product injection date, time, dose and injection site of the most recent dose before each visit will be recorded in the dosing diary.

6.5 Dose modification

The dose will be calculated by the investigator at each visit based on the participant's body weight measured at the visit. This dose will be injected until the next visit. The dosing table in Appendix 8 (Section [10.8](#)) must be used for calculation of the dose and selection of pen strength.

The investigator will communicate the prescribed dose to the participant's parent(s)/participant's LAR.

Modifications to the calculated dose should only be performed as described in Section [6.5.1](#). Dose titration is not allowed.

6.5.1 Dose reduction criteria

If adverse events (AEs) with a probable relationship to the trial product are severe but allow continuation in the study, as judged by the investigator, a dose reduction can be considered at the investigator's discretion. A reduction of the dose leading to a 25% reduction of the current exposure level is recommended (See [Table 6-2](#)). If the AE persists after the first dose reduction, a second dose reduction may be considered. If the AE is not resolved after two dose reductions the participant's treatment may be discontinued according to treatment discontinuation or withdrawal

criteria (see Section [7](#)). Treatment with a reduced dose should be for at least 4 weeks before dose can be resumed to the original planned dose at the investigator's discretion.

In the present study, dose will, furthermore, be reduced, if two consecutive IGF-I measurements confirmed by a re-test are above +3.0 SDS, if it is confirmed that the IGF-I sample is taken according to protocol. If IGF-I SDS exceeds +3.0 SDS at two consecutive visits the investigator will be contacted by Novo Nordisk and requested to reach out to the participant as soon as possible. The participant should be invited for a re-test within 4 weeks to confirm persistent IGF-I levels above +3.0 SDS. Blood samples for the confirmatory measurement of IGF-I should be collected at the end of the dosing interval (day 7 post-dose).

If IGF-I is still elevated above +3.0 SDS in the additional confirmatory measurement, dose reduction to a lower dose level will be required. Treatment with a reduced dose should be for at least 4 weeks before a subsequent IGF-I determination can result in further dose reduction. If the next scheduled visit is less than 4 weeks after the dose reduction was effectuated, the IGF-I result at that visit must NOT be used for evaluation of an additional dose reduction. At the next visit (or at an extra, unscheduled visit which complies with the 4 weeks minimum period), IGF-I will be re-tested.

Details about dose reduction are included below.

In the extension periods of the study, if the IGF-I level is below 1 SDS following dose reduction, the dose can be increased to the previous (higher) dose level.

First dose reduction

The first dose-reduction should be from 0.24 mg/kg/week to 0.21 mg/kg/week (See [Table 6-2](#)). This dose reduction step is expected to provide at least 25% reduction in somapacitan exposure considering the non-linear PK of somapacitan.

Second dose reduction

If, after first dose reduction, IGF-I exceeds +3.0 SDS at two (2) consecutive visits and is confirmed by re-test following the above described process, somapacitan dose should be reduced from 0.21 mg/kg/week to 0.18 mg/kg/week (See [Table 6-2](#)). This dose reduction step is expected to provide an additional 25% reduction in somapacitan exposure considering the non-linear PK of somapacitan.

Continuous persistently elevated IGF-I after two dose reductions

If, after second dose reduction, IGF-I exceeds +3.0 SDS at two (2) consecutive visits and is confirmed by re-test following the above-described process, the participant should be offered individual medical advice by the investigator.

In case of dose reduction, relevant dosing tables must be requested from Novo Nordisk.

Table 6-2 Dose reduction for somapacitan

Original dose (mg/kg/week)	Dose after first reduction (mg/kg/week)	Dose after second reduction (mg/kg/week)
0.24	0.21	0.18

6.5.2 Rationale for dose reduction criteria

In studies including children born SGA, IGF-I levels have been found to range up to +5.6 SDS with 0.067 mg/kg daily GH treatment (n=31)⁴⁵ and up to +5.0 SDS with mean daily GH dose of 0.06 mg/kg (n=23)⁵⁰. Furthermore, in the phase 2 study NN8640-4245 in children born SGA, the IGF-I levels following Norditropin® 0.067 mg/kg/day ranged up to +4.2 SDS (n=13). These studies are conducted with use of approved daily GH doses, and based on the safety outcome of the studies, Novo Nordisk finds it reasonable to suggest the described dose reduction criteria.

6.6 Continued access to study intervention after end of study

When discontinuing trial product, the participant should be transferred to a suitable marketed product at the discretion of the investigator.

If a participant discontinues trial product during the study and is transferred to a marketed product this should be recorded as ancillary therapy according to Section [6.8.1](#).

6.7 Treatment of overdose

Novo Nordisk does not recommend specific treatment for an overdose of somapacitan. In the event of an overdose appropriate supportive treatment should be initiated according to local practice.

Accidental overdose must be reported as a medication error. Intentional overdose must be reported as misuse and abuse, please refer to Section [8.3](#) and Appendix 3 (Section [10.3](#)) for further details.

In the event of an overdose, the investigator should closely monitor the participant for overdose-related AEs/SAEs.

For more information on overdose, also consult the somapacitan investigator's brochure (IB).

6.8 Concomitant therapy

Changes in concomitant medication must be recorded at each visit. If a change is due to an AE/SAE, then this must be reported according to Section [6.8.1](#).

From visit 2 onwards, initiation of treatment that may affect growth is not recommended. Relevant medication not recommended during the study is listed in Section [6.8.2](#). However, medical judgement should always be according to the investigator's discretion.

Any medication or vaccine (including over-the-counter or prescription medicines, recreational drugs, vitamins, and/or herbal supplements) other than the trial product, that the participant is receiving at the time of the screening visit or receives during the study must be recorded along with:

- Trade name or generic name
- Primary indication

- Start and stop dates
- Frequency
- Dose

Changes in concomitant medication or therapy must be recorded at each visit. If a change is due to an AE, then this must be reported according to Section [8.3](#).

All previous growth promoting treatment must be recorded until visit 2.

6.8.1 Ancillary therapy

Ancillary therapy is defined as any GH treatment (other than trial product) and IGF-I medication that the participant receives. Ancillary therapy is not allowed, but participants who discontinue trial product can start treatment with a marketed GH product as outlined in Section [6.6](#).

Any ancillary therapy must be recorded along with:

- Trade name or generic name
- Start and stop dates

6.8.2 Medication with a special focus

Medication with a special focus is defined as medication that can potentially impact the evaluation of the primary endpoint, due to either directly growth promoting or -inhibiting effects.

In the present protocol these are defined:

- ADHD medication (ATC code: N06BA04; methylphenidate)
- Glucocorticoid therapy: (ATC code: H02AB)
- Sex steroids (ATC code: G03A; G03C; G03F) and aromatase inhibitors (ATC code: L02BG)
- Insulin treatment (ATC code: A10A)

Any medication with a special focus must be recorded along with:

- Trade name or generic name
- Primary indication
- Start and stop dates
- Frequency
- Dose

7 Discontinuation of study intervention and participant discontinuation/withdrawal

Discontinuation of specific sites or of the study as a whole is detailed in Appendix 1 (Section [10.1.11](#)).

7.1 Discontinuation of study intervention

Study intervention may be discontinued at any time during the study at the discretion of the participant or at the discretion of the investigator for safety, behavioural, compliance or administrative reasons.

Efforts should be made to have the participants who discontinue study intervention attend visit 7 to collect the required data for the analysis of the primary endpoint. Only participants who withdraw consent will be considered as withdrawn from the study. Participants must be informed about the continued scientific importance of their data, even if they discontinue study intervention.

The study intervention must be discontinued, if any of the following applies for the participant:

1. Pregnancy.
2. Intention of becoming pregnant.
3. Simultaneous use of an approved or non-approved investigational medicinal product in another clinical study.
4. Tumour development.
5. Near adult height is reached (Near adult height (NAH) is defined as HV below 2 cm/year calculated over a period of at least 9 months AND for males: have reached a bone age of above or equal to 16 years; for females: have reached a bone age of above or equal to 14 years). If bone age is not available, then NAH is defined as HV below 2 cm/year calculated over a period of at least 9 months AND a chronological age of ≥ 17 years for males and a chronological age of ≥ 15 years for females.
6. Evidence of closure of the epiphyseal growth plates.

See the flowchart for data to be collected at the time of study intervention discontinuation (early discontinuation visit) and follow-up and for any further evaluations that need to be completed.

At visit 17A/98 (Discontinuation visit) the following assessments are not applicable if performed within the last 6 months:

- X-ray for bone age assessment
- ECG
- TTE

The primary reason for discontinuation of study intervention must be specified in the CRF, and final trial product accountability must be performed. Discontinuation of treatment must be registered in RTSM.

Trial product discontinuation prior to visit 7

If a participant discontinues treatment prior to visit 7, the discontinuation visit (Visit 17A) should be performed at least 7 days after the last dose of trial product and prior to starting treatment with a

marketed product. The follow up visit (Visit 18) should be performed a minimum of 30 days after the last dose of trial product.

Although the treatment has been discontinued, the participant should continue to follow the planned visit schedule until the visit 7 (26 weeks) in order to collect data for the primary endpoint and should then be withdrawn.

If the participant or participant's parent(s)/participant's LAR refuses to attend the planned visit schedule, then visit 7 is of utmost importance to attend. Visit 7 should be performed on planned visit date compared to baseline.

At visits after visit 17A (Discontinuation visit) the following assessments are not applicable for participants that discontinue trial product:

- Study intervention
- Drug accountability (when completed for the participant)
- PK sampling
- Collection of technical complaints
- Injection site reactions
- Medication errors
- COA questionnaires

Trial product discontinuation between visit 7 and visit 17

If a participant discontinues treatment at or between visit 7 and visit 17 the treatment discontinuation visit (Visit 17A) should be performed at least 7 days after the last dose of trial product and prior to starting treatment with a marketed product.

The follow-up visit should be performed a minimum 30 days after the last dose of trial product and the participant should then be withdrawn from the study.

Trial product discontinuation after visit 17

If a participant discontinues treatment after visit 17, the treatment discontinuation visit (visit 98) should be performed at least 7 days after the last dose of trial product and prior to starting treatment with a marketed product. The follow-up visit should be performed a minimum 30 days after the last dose of trial product and the participant should then be withdrawn from the trial.

7.1.1 Temporary discontinuation of study intervention

If treatment is temporarily discontinued due to an AE, treatment can be resumed in accordance with Section [6.5.1](#).

7.1.1.1 Hepatic events requiring temporary discontinuation of study intervention

Temporary discontinuation of study intervention is required for hepatic events, defined as:

- ALT (or AST) $\geq 3 \times$ upper limit of normal (ULN) and total bilirubin $\geq 2 \times$ ULN ($> 35\%$ direct bilirubin) or ALT (or AST) $\geq 3 \times$ ULN and international normalised ratio (INR) > 1.5 (if INR measured), which may indicate severe liver injury (potential Hy's law)**

- ALT (or AST) $\geq 3 \times$ ULN with the appearance of fatigue, nausea, vomiting, anorexia, abdominal pain or tenderness, fever, rash, and/or eosinophilia (>5%).

**Please note that such an event must be reported as a SAE using the important medical event criterion if no other seriousness criteria are applicable (as described in Appendix 3 (Section [10.3](#))).

Temporary discontinuation of study intervention is also required in case of abnormal liver laboratory values not meeting protocol-specified discontinuation criteria, if the investigator deems that it is in the best interest of the participant.

Study intervention can be restarted only if an alternative aetiology is definitively identified, and liver blood parameters have returned to pre-event levels. If an alternative aetiology is not definitively defined and/or liver blood parameters have not returned to pre-event levels, drug-induced liver injury (DILI) cannot be excluded, and study intervention must be permanently discontinued.

Please see Appendix 6 (Section [10.6](#)) for follow-up information on hepatic safety.

Please also see the criteria for an AE and Hepatic Event form in Appendix 3 (Section [10.3.3](#)).

7.2 Participant discontinuation/withdrawal from the study

A participant may be discontinued from the study at any time at the discretion of the investigator for safety, behavioural, compliance or administrative reasons.

A participant may withdraw consent at any time at his/her own request or at the request of the participant's parent(s)/participant's LAR.

If a participant withdraws consent or is withdrawn by the investigator prior to receipt of study intervention, he/she will not be asked to have any follow-up assessments performed. The following data must be collected: Demography, eligibility criteria, date of informed consent, date of screening and the date when participant's participation ended. The end of study form must be completed.

If a participant withdraws consent or is withdrawn by the investigator after receipt of study intervention before visit 17, the investigator must ask the participant if he/she is willing, as soon as possible, to have assessments performed according to visit 17A. Furthermore, the investigator must ask the participant if he/she is willing to come for a follow up visit (Visit 18) a minimum of 30 days after last dose of trial product. See the flowchart (Section [1.2](#)) for data to be collected.

If a participant withdraws consent after visit 17, the investigator must ask the participant if he/she is willing, as soon as possible, to have assessments performed according to visit 98 and the follow-up visit (visit 99). See the flowchart (Section [1.3](#)) for data to be collected.

Final trial product accountability must be performed even if the participant is not able to come to the site. Discontinuation of treatment must be registered in RTSM.

If the participant withdraws consent, Novo Nordisk may retain and continue to use any data collected before such a withdrawal of consent for the purpose of the study or scientific research.

If a participant withdraws from the study, he/she may request destruction of any samples taken and not tested, and the investigator must document this in the medical record.

Although a participant is not obliged to give his/her reason(s) for withdrawing, the investigator must make a reasonable effort to ascertain the reason(s), while fully respecting the participant's rights. Where the reasons are obtained, the primary reason for withdrawal must be specified in the CRF.

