7.2.1 Replacement of participants

If a participant discontinues study intervention, withdraws consent or is withdrawn by the investigator, he/she will not be replaced.

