- The population targeted by the clinical question: The treatment effect will be assessed separately for each group of previously treated (yes/no) in the four populations (SGA, TS, NS or ISS).
- Endpoints:
 - Height velocity from baseline (week 0) to visit 7 (week 26)
 - Change in Height SDS from baseline (week 0) to visit 7 (week 26)
 - Change in Height Velocity SDS from baseline (week 0) to visit 7 (week 26)

Remaining intercurrent events: The 4 intercurrent events ‘dose reduction due to IGF-I or AE’, ‘treatment discontinuation for any reason’, ‘initiation of ancillary therapy’ and ‘medication with a special focus’, are all addressed by the treatment condition of interest attribute. There are no remaining intercurrent events.

- Population-level summary: Mean change

Rationale for estimands: The estimands assess the expected benefit a future population (SGA, TS, NS or ISS) can achieve if prescribed somapacitan. By not placing any restrictions on treatment adherence, these estimands aim to obtain a difference as close as possible to the one that can be

expected in clinical practice, provided that the dose reduction, treatment adherence and use of ancillary therapy in the study reflects what would be seen in clinical practice.

The supportive secondary estimands will be evaluated based on all participants where both baseline and week 26 data are collected. To support the supportive secondary estimands SD, median, min and max values will also be derived for the supportive secondary endpoints.

Change in IGF-I SDS and Change in IGFBP-3 SDS

The clinical question of interest for the supportive secondary efficacy endpoints Change in IGF-I SDS and Change in IGFBP-3 SDS from baseline (week 0) to visit 7 (week 26) are: What is the mean change after 26 weeks of somapacitan treatment within each group of previously treated (yes/no) in the four populations (SGA, TS, NS or ISS) patients while on treatment regardless of dose reduction due to IGF-I or AE or medication with a special focus?

The supportive secondary estimands are defined for each of the four populations (SGA, TS, NS or ISS) with five attributes:

- The treatment condition of interest is defined as somapacitan regardless of dose reduction or medication with a special focus.
- The population targeted by the clinical question: The treatment effect will be assessed separately for each group of previously treated (yes/no) in the four populations (SGA, TS, NS or ISS)
- Endpoints:

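### Protocol Sections 7.1 and 7.2 conflict on who may leave the study, so investigator removal for behaviour or compliance before visit 7 can take poor compliers out of week-26 growth summaries meant to ignore adherence

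*Protocol*

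**What the plan says.** **Stopping drug (Protocol Section 7.1).** "Study intervention may be discontinued at any time during the study at the discretion of the participant or at the discretion of the investigator". The permitted grounds are four: safety, behaviour, compliance and administration. The section adds: "Only participants who withdraw consent will be considered as withdrawn from the study". A child who stops before visit 7 is to stay on the visit schedule to week 26, and visit 7 is singled out as the one to attend if the rest are refused.

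**Leaving the study (Protocol Section 7.2).** The same four reasons appear as grounds for leaving the study itself: "A participant may be discontinued from the study at any time at the discretion of the investigator for safety, behavioural, compliance or administrative reasons". The section then sets follow-up for this case: "If a participant withdraws consent or is withdrawn by the investigator after receipt of study intervention before visit 17", the child is asked to attend visit 17A as soon as possible and visit 18 at least 30 days after the last dose. Visit 7 is not requested. Section 7.2.1 recognises the same category: "If a participant discontinues study intervention, withdraws consent or is withdrawn by the investigator, he/she will not be replaced".

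**Growth estimands (Protocol Section 9.3.3; SAP Section 4.3.2.2).** Height velocity, change in height SDS and change in height velocity SDS follow a treatment-policy strategy, whatever the reason for stopping treatment. The rationale reads: "By not placing any restrictions on treatment adherence, these estimands aim to obtain a difference as close as possible to the one" expected in practice. The estimation rule is: "The supportive secondary estimands will be evaluated based on all participants where both baseline and week 26 data are collected". The in-study data points set (Protocol Section 9.2; SAP Section 3) ends at visit 7 or last study contact, whichever is earlier. Neither document plans imputation or a missing-data sensitivity analysis for these endpoints.

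**The concern.** A site with a non-compliant child before week 26 can follow either section, with opposite results for the data. Under 7.1 drug may stop and the week-26 height is still measured. Under 7.2 the child may leave the study and the height is lost. The second route selects on adherence, the very factor that the estimand says must not restrict the population. The reported mean would then lean towards compliers while carrying a treatment-policy label. Results are reported by indication and by previous treatment (yes/no), so the cells are small and a single removal can be visible.

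**Working it through.** There is no plan figure to reproduce: Protocol Section 9.5 reports no formal sample size calculation, and no dropout or removal rate is stated.

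**Step 1: trace one child.** A child is dosed and then removed by the investigator for compliance before visit 7.
- Under 7.2 the visits requested are 17A and 18. A height at 17A is taken at the time of leaving and is not a week-26 value.
- The in-study set closes at last study contact.
- The estimation rule needs both a baseline and a week-26 value, so the child is excluded.
- Under 7.2.1 nobody takes the child's place.

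Had the same child been handled under 7.1, the visit 7 height would be collected and counted.

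**Step 2: size of the shift.** Let *p* be the share of a group that is lost and *d* the mean height velocity of the retained children minus what the lost children would have had at week 26. The full-group mean is the retained mean minus *p* × *d*, so

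bias of the observed-case mean = *p* × *d*.

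Inputs:
- Planned completers: at least 10 per indication. Planned enrolment: up to 50, or 50/4 = 12.5 per indication if even (Protocol Section 9.5).
- Cells: an even split by previous treatment is assumed, giving 10/2 = 5 or 12.5/2 ≈ 6 children before the loss.
- Gap *d*: not in the documents. I assume 2 to 4 cm/year, and also show 0 and −2.

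| One child lost from | *d* = −2 | *d* = 0 | *d* = 2 | *d* = 4 |
|---|---|---|---|---|
| cell of 5 (*p* = 1/5) | −0.40 | 0 | 0.40 | 0.80 |
| cell of 6 (*p* = 1/6) | −0.33 | 0 | 0.33 | 0.67 |
| indication of 10 (*p* = 1/10) | −0.20 | 0 | 0.20 | 0.40 |

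All entries are in cm/year.

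**Step 3: other endpoints.** The primary estimand counts adverse events on treatment, up to 14 days after the last dose, as a rate per 100 patient-years. A removed child contributes events and exposure until then, so this route affects it little.

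**The case against.** **The conflict may be softer than it looks.** The 7.1 sentence on consent sits in a paragraph about children who stop drug, and can be read as saying only that stopping drug is not in itself withdrawal. Nor is it applied strictly elsewhere: 7.1 has children who stop early withdrawn after visit 7, and 7.3 counts loss to follow-up as withdrawal. This stands as a reading, but it leaves 7.2 open as a way out of the study before visit 7.

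**Removal may be rare.** Section 7.2 permits it and does not require it. Exclusion criterion 11 screens out families judged likely to be non-compliant, Section 6.4 answers suspected non-compliance with a documented dialogue, and a poor complier who stays to visit 7 is counted. All of this lowers the likely frequency; none of it closes the route.

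**A reader might infer that the growth results are biased upward.** The documents do not support that as a fact. They give no removal rate and no growth difference for poor compliers. A child who stops trial product may start a marketed growth hormone (Sections 6.6 and 6.8.1), and this estimand counts growth under ancillary therapy, so the gap at week 26 could be small. At zero gap there is no bias, and a reversed gap gives a downward one.

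**Little depends on these endpoints.** They are supportive and descriptive, in an uncontrolled study with no hypothesis tests. That is correct and limits the weight of the point. Losses through consent withdrawal or lost contact would also remain after the change below.

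**Conclusion.** The inconsistency is real and has a definite data consequence: a child removed by the investigator for behaviour or compliance before visit 7 is missing from three growth summaries whose estimand disregards adherence. Upward bias is the plausible direction, since less drug should mean less growth, but it is conditional on those children growing less by week 26.

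As an illustration, one loss moves a cell mean by about 0.3 to 0.8 cm/year, or the mean of an indication of 10 by 0.2 to 0.4 cm/year. This rests on the assumed gap of 2 to 4 cm/year and, for the cells, on an even split by previous treatment. It is not a prediction of what will happen in this trial. The primary safety result is not put in doubt.

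**What to change.** Reconcile Section 7.2 with Section 7.1. State that, before visit 7, investigator discontinuation for behavioural or compliance reasons does not end study follow-up, and that the child is followed to visit 7 for height unless consent is withdrawn. The rules on stopping treatment need not change. The cost is a sentence or two at the next amendment, with no new visit, because visit 7 is already planned for children who stop drug.

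The amendment may come too late for many children. Extension period II lasts up to 91 weeks after week 156 and ends by October 2027; 156 + 91 = 247 weeks, about 4.7 years, which puts the earliest starts around early 2023. The documents do not give enrolment status. For children already past visit 7, the clinical study report should list investigator withdrawals before visit 7 by reason (Section 7.2 already has the primary reason recorded in the CRF where it is obtained) and qualify the treatment-policy label if there are any. This costs one listing.
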